3.7. Participant Withdrawal Criteria

Participants will be withdrawn from the study treatment if they meet one or more of the following criteria:

1. CGI-I ≥ 6 on two consecutive visits
2. If they become pregnant during the study
3. If they have blood pressure above 99th percentile for age, gender, and height on two consecutive visits (*range in accordance with the Fourth Report on the Diagnosis, Evaluation, and Treatment of High Blood Pressure in Children and Adolescents (U.S. Department of Health and Human Services)⁵³)
4. If they have blood pressure above the 99th percentile for age, gender, and height on two consecutive visits
5. If they experience an adverse event that is deemed by the Medical Independent Evaluator (IE) to be an unacceptable safety risk
 - o If the Study clinician feels it is in the participant's best interest to discontinue the study treatment

4. Study Assessments

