*Clinical Global Impressions – Improvement Scale - Global (CGI-I)*⁵⁴. The CGI-I employs a seven point (1 = very much improved to 7 = very much worse) to determine the patient's improvement in response to treatment. The CGI-I has been successfully used as an outcome measure in previous psychopharmacology trials including the RUPP trial of risperidone in children with ASD, and the STAART funded citalopram trial. The rating convention for assigning CGI scores is to use all available data including direct observation, scales, and patient report to inform clinical judgment. CGI-I, Global will be used to evaluate safety, with the requirement that individuals scoring CGI of 6 or greater for 2 or more weeks be discontinued from the study and provided with appropriate referrals. CGI ratings will be made by unblinded clinicians conducting safety evaluations and blinded raters.

Blinded CGI-I ratings will incorporate semi-structured questions to evaluate social conversational and social behavioral skills. Questions will be based on the Bates & Reilly conversational task (Reilly, Bates, & Marchman, 1998). Blinded CGI ratings will be recorded to code narrative discourse and quality in collaboration with the social communication lab of [name]. Social Functioning

2. Social functioning

- a. *Social Skills Improvement System (SSIS)*. The SSIS is an informant-report that evaluates social skills, problem behaviors, and academic competence in youth ages 3-18 years old. The SSIS is a multi-rater with reports provided by caregivers, teachers, and students. The form takes 10-25 minutes to complete. The scale is designed to identify social impairments for intervention development and tracking.

3. Quality of Life

- a. *Caregiver Strain*⁵⁹. The CSQ assess family stress and was developed for caregivers of children with developmental disabilities.

Exploratory Outcome Measures

1. Social Function

- a. *Autism Impact Measure*⁶⁰. The AIM is a 25-item caregiver report assessment of the frequency and impact of core ASD symptoms in children with ASD. This new measure is designed to assess recall of core symptoms within two-week intervals and will be used as an exploratory measure of changes in core ASD symptom presentation in this study.

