4.3. Safety Assessments

Adverse events will be systematically reviewed by study clinician and each study will have a back-up physician to assess safety. The study clinician will also do a general inquiry about health, other medications, and visits to medical care providers since the last visit. The following safety measures will be completed either in-person or may take place virtually via a HIPAA compliant platform (i.e. Zoom) if needed to reduce the amount of in person interaction between study team and participant.

- *Clinical Global Impressions – Improvement Scale – Global (CGI-I)*. The CGI-I employs a seven point (1 = very much improved to 7 = very much worse) to determine the patient's improvement in response to treatment. The CGI-I has been successfully used as an outcome measure in previous psychopharmacology trials including the RUPP trial of risperidone in children with ASD, and the STAART funded citalopram trial. The rating convention for assigning CGI scores is to use all available data including direct observation, scales, and patient report to inform clinical judgment. CGI-I, Global will be used to evaluate safety, with the requirement that individuals scoring CGI of 6 or greater for 2 or more weeks be discontinued from the study and provided with appropriate referrals.
- *Adverse event rating form*
This is a semi-structured interview that has been modified to assess OXT specific side effects for a recently completed pediatric trial of sustained oxytocin treatment in ASD ⁵². It contains a general inquiry, drug-specific queries, as well as several questions about daily activities (e.g., sleep, appetite, energy level, bowel and bladder function). This instrument has been widely used in other autism related clinical trials. In addition to these measures, vital signs (heart rate, blood pressure) will be measured biweekly at the following visits: screening, baseline/week 1, week 3, week 5, week 7, week 9, week 11, week 12, week 16, and week 24 (or another biweekly schedule depending on start days/dates) Standardized procedures will be used for all physical measurements. We will attempt to do vital signs following a 4 minute period of rest, with the participant seated. Height and Weight will be taken at screening, baseline, Week 12, and Week 24 with all outer wear and shoes removed at every visit.

5. Study Treatment

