Caregiver reports on the ABC, PDDBI-SV, Griffith Empathy Scale, Children's Communication Checklist, CASI-5, Caregiver Strain, Vineland 3, SRS-2, RBS-R, and AIM will be collected at midpoint along with CGI-I ratings (blinded). Ratings may be conducted +/- 7 days from week 6 group depending on family schedules.

Week 12 (Endpoint)

The end of treatment visits occurs at Week 12 (to take place within \pm 7 days from the target date). At these visits, blood work, vital signs, temperature, height, weight, and an ECG will be completed. In addition, participants will undergo a series of assessments, which are anticipated to take approximately 4-6 hours to complete. The visit can be split into as many as three visits if this is better for the participant. The following measures will be completed: the CGI-I (Global and Social), the AE rating form, the Bates & Reilly Conversational Task, the CY-BOCS, Let's Face It, the RMET, the CASI-5, the RBS-R, the SRS, the ABC, the BFRT, the BASC-3, the PDDBI-SV, the Griffith Empathy Scale, the CCC, the Caregiver Strain, the DANVA2, the TAT, , and the GEMEP emotion recognition test, and sensor-based social-communication monitoring tests.

Week 16 & Week 24 (Maintenance visits 1 & 2)

There will be an additional follow-up appointment 12 weeks (\pm 7 days) after the participant stops taking the study drug. This visit is primarily to examine safety of OXT discontinuation, and look for possible maintenance of any favorable effects of ION-, and longer term safety. The assessments completed during this visit are identical to the Week 12/end of treatment visit.

Termination Visit: A participant may voluntarily withdraw from the study at any time. The PI has the right to discontinue a subject from this study or withdraws a participant from the study at any time. Every effort will be made to obtain information on subjects who withdraw. Participants who discontinue study drug prematurely will be asked to return to the clinic and complete all end of study safety lab work (week 12 blood work).

Participants will also be asked to complete all endpoint study procedures on their final visit before withdrawal to allow for true intent to treat analysis.

Missed Visits and Visit Windows

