8.8. Statistical analysis

Specific Aim 1 & Exploratory Aim 1: Safety and tolerability will be analyzed by analyzing for group differences on total scores and domains of the AE form and satisfaction surveys respectively. Efficacy analysis will be follow analytic procedures used to derive social behavior and social cognition composites for the Seaver-NETT RCT¹⁶. First, a principal components analysis with varimax (orthogonal) rotation will be conducted on subscales of the primary social behavior measures - Griffith Empathy Scale and CCC-2; and raw total scores on primary social cognition outcomes – RMET and DANVA2. The PCA is used to develop composite scores in a field with no viable outcomes for higher-order core social impairments as well as to minimize floor and ceiling artifacts, effects of variability in response, and other sources of measurement error. Variables with high factor loadings for subscales will be entered into composite score development for the social cognition and social behavior composites. Missing, invalid, and/or incomplete data (i.e. more than 30% items missing when not pre-defined by scale) will be excluded from the factor analysis.

A linear mixed model analysis will be conducted on all participants with at least two of four available time points (Wk 0, Wk 12, 1-mon, 3-mo). Composite scores of co-primary outcomes social behavior and social cognition will be used as the response variable; treatment condition, time, and condition * time interactions will be covariates. Verbal IQ will also be entered into the model in exploratory moderator analyses. We will estimate effect sizes (Cohen's d) and confidence intervals (95%) acknowledging the likelihood that analyses may not permit definitive conclusions given the likely size of the confidence intervals.

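### An assessment at withdrawal is said to allow intention-to-treat, but nothing commits to Week 12 outcomes for children who stop treatment or says how early values are analysed

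*Protocol*

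**What the plan says.** Protocol 5.2 fixes the endpoint in time: "The end of treatment visits occurs at Week 12", within 7 days of the target date. Its Termination Visit paragraph then makes three statements about children who stop early:

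- a general promise: "Every effort will be made to obtain information on subjects who withdraw";
- a specific recall: "Participants who discontinue study drug prematurely will be asked to return to the clinic and complete all end of study safety lab work";
- the efficacy rule, under which they are also asked to "complete all endpoint study procedures on their final visit before withdrawal to allow for true intent to treat analysis".

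The protocol uses two different words for what happens when CGI-I reaches 6. Section 3.7 lists "CGI-I ≥ 6 on two consecutive visits" as a reason for withdrawal from study treatment. Section 4.2 requires that "individuals scoring CGI of 6 or greater for 2 or more weeks be discontinued from the study", and 4.3 repeats that such children "be discontinued from the study and provided with appropriate referrals". Section 8.5 (Stopping procedures) says only that subjects may be withdrawn, and lets a child who remains at 6 or 7 be discussed with the medical monitor for approval to continue.

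On analysis, Protocol 8.8 runs the linear mixed model on "all participants with at least two of four available time points (Wk 0, Wk 12, 1-mon, 3-mo"). The SAP (Data Analysis) specifies condition, time and their interaction with a random effect for participant. It has item-level missing-data rules and outlier rules. It says nothing about assessments made at early termination and gives no sensitivity analysis for missing outcomes.

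**The concern.** Intention-to-treat compares the randomised groups on the outcome at the planned time, whatever treatment was actually taken. An assessment at the moment of leaving measures something else: the child's state after however many sessions were completed.

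The difference matters here because the curriculum is sequential. Protocol 5.1 places theory of mind in the last module, so a child who leaves before then has not had the training closest to the mental-state task (RMET) in the social cognition composite. A child who leaves at Week 4 is assessed 12 − 4 = 8 weeks early, far outside the 7-day window.

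The reasons for leaving are also plausibly related to outcome: clinical worsening, adverse events, blood pressure, noncompliance. If early values are used as the endpoint, the estimate mixes Week 12 outcomes with outcomes at an outcome-dependent earlier time. If they are discarded, some randomised children leave the analysis. In both cases the protocol claims a property that its procedure does not provide.

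**Working it through.** **Step 1. What can happen to an early assessment.** Take a child with a baseline, an assessment at withdrawal in Week 4, and nothing later.

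| Handling | Consequence under Protocol 8.8 |
|---|---|
| Recorded as Week 12 | Child has two of four time points and is analysed, but with a Week 4 value in the Week 12 position |
| Not assigned to a time point | Child has one of four time points and is excluded, although randomised |
| Entered at actual week | Keeps the child and the correct timing, but neither document provides for it |

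Only the third is satisfactory, and even that does not supply the missing Week 12 outcome.

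**Step 2. Is Week 12 efficacy follow-up promised elsewhere?** The recall of children who stop the drug names safety laboratory work. The general promise names no measure and no date. The follow-up visit in 5.2 is timed at 12 weeks after the drug is stopped and repeats the Week 12 battery. For a child who stops at Week 4 it would fall at 4 + 12 = Week 16. Control children have no drug-stop date at all. Appendix A lists Weeks 12, 16 and 24 but does not say that they continue after treatment is stopped. So no text commits to on-schedule Week 12 efficacy data for a treatment stopper.

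**Step 3. The plan's own figure.** Protocol 8.9 gives 25 per group with 5% attrition, a difference of 0.40, SD of differences 0.670, two-sided 0.05 and 80% power. A one-sample (paired) t-test reproduces this: the noncentrality is (0.40/0.670) × √24 = 2.92, giving 80.0% at n = 24. With 25 × 0.95 = 23.75 it is 79.5%. A two-group t-test at 25 per group gives 54%. That is a separate matter; 0.40 and 0.670 are used below only as a scale.

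**Step 4. Scale if early values sit in the Week 12 position.** Let d be the share of an arm that leaves early. The 5% is the protocol's figure; 10% and 20% are assumptions.

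*(a) Informative values in one arm.* Assume that those leavers' early values differ from their Week 12 values by s SDs. Shift in the difference = d × s × 0.670.

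| d | s = 0.25 | s = 1.0 | Share of 0.40 |
|---|---|---|---|
| 5% | 0.008 | 0.034 | 2% to 8% |
| 10% | 0.017 | 0.067 | 4% to 17% |
| 20% | 0.034 | 0.134 | 8% to 34% |

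For example, 0.05 × 1.0 × 0.670 = 0.0335, and 0.0335/0.40 = 8.4%.

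*(b) Dilution, same attrition in both arms.* Assume that leavers have reached a fraction f of the Week 12 effect. Estimated effect = 0.40 × [1 − d(1 − f)]. At d = 5% this runs from 0.380 (f = 0) to 0.395 (f = 0.75); at d = 20%, from 0.320 to 0.380.

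**Step 5. Against sampling error.** With 35 per arm (Phase 2, n = 70, allocated 1:1), the standard error is 0.670 × √(2/35) = 0.160. A shift of 0.0335 is 0.0335/0.160 = 0.21 standard errors; a shift of 0.134 is 0.84.

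**The case against.** The best defence is that the plan never says the early value becomes Week 12. A reader might infer last observation carried forward from the wording about endpoint procedures, but no sentence codes it that way, and the planned analysis is a mixed model, which could in principle take a value at any week. That stands. What can be shown is the absence of a rule, and that the two natural ways of filling the gap both fail.

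A reader might also infer that children who stop the drug are recalled for safety laboratory work and nothing else. The documents do not support that. The next sentence asks for the endpoint procedures as well, and there is a visit 12 weeks after the drug is stopped. The gap is narrower: none of this is tied to Week 12.

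It is tempting, too, to assume that early stopping falls mainly on the oxytocin arm. The withdrawal criteria in 3.7 apply to all participants, 5.2 has vital signs and adverse event ratings done in all groups, and 5.3 collects adverse event data across all groups. Section 1 says intranasal oxytocin has not been found to affect blood pressure substantially. Imbalance between arms is possible but not shown. Nor does any passage link the withdrawal triggers directly to the caregiver scales and emotion-recognition tests that form the composites, so outcome-related stopping is plausible rather than established.

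Finally, an assessment at withdrawal does preserve data. For a family that leaves the study it may be the only post-baseline information obtainable. That is a good reason to keep it, but not to call it intention-to-treat. The pilot's own caution about wide confidence intervals does not answer the point either, because bias is not reflected in the interval.

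**Conclusion.** The point holds in this form: the assessment at withdrawal does not by itself deliver the intention-to-treat analysis claimed for it, no text commits to on-schedule Week 12 efficacy outcomes for children who stop treatment, and neither document says how early values are analysed. The CGI-I passages in 3.7, 4.2, 4.3 and 8.5 disagree on whether a child leaves treatment, leaves the study or may continue with approval. The sponsor must reconcile them, because the answer determines who is still available for follow-up.

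The likely size is modest. At 5% attrition the shift is at most about 8% of the planned 0.40 for a full 1 SD change confined to one arm; it becomes material (up to about 34%) only if attrition nears 20%. These figures rest on assumed shifts, on early values being used as Week 12, and on 0.670 as the SD. A reader might reach 12.5% by dividing 0.05 SD by 0.40, but that mixes units: it needs an SD of 1 on the scale of the 0.40, which the protocol does not state. The change is worth making because it removes an avoidable bias at little cost, not because the trial depends on it.

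**What to change.** In Protocol 5.2 and the SAP:

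1. Define stopping study treatment and withdrawing from the study as separate events, and record each with its date and reason. Reconcile the CGI-I passages accordingly.
2. Ask every randomised child who stops treatment, in either arm, to complete the already scheduled Week 12, 16 and 24 caregiver forms and blinded assessments unless consent is withdrawn. Time these from the group schedule, not from the last dose.
3. Use remote collection where the protocol allows it. Blinded CGI ratings may already be done by video (3.6), and both social behavior measures are caregiver questionnaires. No remote option is stated for the computerised RMET and DANVA2, so these may need a visit.
4. Keep the assessment at withdrawal for families who leave the study. Record its actual date, analyse it at its actual week and never as Week 12, and state how the two-of-four time-point rule treats such a child.
5. Add a sensitivity analysis for missing Week 12 outcomes.

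If these changes are not made, remove the intention-to-treat label from 5.2. The cost is wording in two documents and a few already scheduled visits: 5% of 35 is about 2 children per arm.

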5.3. Treatment Fidelity and Compliance

Training

Licensed doctoral-level therapists and assistant therapists will be trained by the treatment developers (Drs. [name] & Drs. [name]) using the manuals developed for Seaver-NETT. Training procedures include manual review, watching videos and weekly supervision meetings with the developers.

Safety evaluations will be conducted by a Medical Independent Evaluator (IE), i.e. licensed child and adolescent psychiatrists and/or doctoral-level nurse practitioners, with experience using the AE rating form. Training on study procedures for all clinicians will occur through a protocol review including safety evaluations and specific modifications to the AE rating form for OXT treatment. AE data will be collected across all groups. In addition, parents will be trained to administer OXT in the NETT-OT condition during the baseline visit using written instructions and in-vivo practice with placebo. Procedures are adopted from the on-going SOARS-B trial.

Neurocognitive Independent Evaluators (IE) will be trained on study assessments including the following: Reading Mind in Eyes Test (RMET), Diagnostic Analysis of Nonverbal Accuracy-2 (DANVA2), Test, Trustworthiness of Faces test, and the adapted Thematic Apperception Test.

Fidelity and Compliance

Behavioral intervention: Fidelity

Treatment fidelity ratings for the behavioral intervention component will occur weekly through use of treatment fidelity checklists completed by raters blind to study hypotheses. Checklists developed in the Seaver-NETT RCT will be used in the current trial and are available for both behavioral intervention conditions, NETT and facilitated play. Raters are trained to 80% reliability prior to independent coding. Feedback is provided on a weekly basis to lead therapists in each condition.

Medication Compliance

Compliance in ION will be measured by providing a diary where the participant and/or parent(s)/legal guardian will note every dose after they take it, at what time they took it, and whether they have any comments. Homework and behavioral rehearsal of assigned weekly activities will also be recorded on the compliance log. In the case of non-compliance (i.e. 1 of 4 weekly doses missed) the Study clinician will review administration of medication and schedule of doses with the participant and will problem solve with the participant to improve compliance at the next visit. Compliance logs and homework can be completed via paper form or virtually on Google Classroom.

In addition, compliance will be assessed research staff who will weigh the bottles each time they are returned. At the end of the study, research staff will assess compliance by comparing the weight of the bottle before dispensing to the weight measured after the bottle was returned to the study team.

6. Laboratory Evaluations

6.1. Clinical Laboratory Evaluations

Clinical laboratory evaluations will be conducted at screening and Week 12.

- Total blood collected is 8.5 ML in SST tube at each time point –screening and week 12.
 - Chemistry Panel: The chemistry panel will include glucose (random, non-fasting), CO₂, CL, K, Na, Creatinine, BUN, Mg

Confidential

Rush University Medical Center

- Routine Hematology
- Liver Profile: AST, ALT
- Urinalysis

7. Ethical Considerations

7.1. Ethics Approval

This protocol and any amendments will be submitted to the Rush Institutional Review Board (IRB) for formal approval of the study conduct.

7.2. Informed Consent

Consent will be obtained by the PI or another delegated research staff member prior to participation in the study and conduct of any study-specific procedures, but after the study has been described and all information given to the participants and their caregivers, as per FDA and IRB policy. This will be done on the first day of screening. It will be the responsibility of the PI to ensure that potential participants understand the extent of their role in the research. Specifically, the written consent and child assent documents will be read through with all potential participants and his/her parent(s)/legal guardian(s), and focus will be placed on potential risks and benefits associated with study participation as well as any alternatives to participating in the research. Most notably, participants and parent(s)/legal guardians will be informed that a participant's opportunity to receive treatment will not depend upon research participation. In addition, the PIs will try to foster an open exchange of information, encouraging potential participants and their families to discuss study particulars and ask questions prior to research involvement; to take a copy of the consent form home to discuss with family and friends, if desired; and to continue asking any questions that might arise during participation. Details on written consent and child assent forms will be presented in simple language approved by the IRB. All key personnel are PHIPPA trained. For children and adolescents not capable of consenting, we will obtain written consent from the parent(s)/legal guardian, and assent from the child. Both consent and assent are required for participation in the study if the participant is unable to consent but able to provide assent. Informed consent review can be completed virtually, as needed, however informed consent signature can only be obtained in person.

